10.2.2 Methods of Measurement

CT and MRI are the best currently available and reproducible methods to measure target lesions selected for response assessment. Conventional CT and MRI should be performed with cuts of 10 mm or less in slice thickness contiguously. Spiral CT should be performed using a 5 mm contiguous reconstruction algorithm. This

applies to tumors of the chest, abdomen and pelvis. For accurate objective response evaluation, ultrasound should not be used to measure tumor lesions. However, ultrasound is a possible alternative to clinical measurements of superficial palpable lymph nodes, subcutaneous lesions and thyroid nodules. Ultrasound might also be useful to confirm the complete disappearance of superficial lesions usually assessed by clinical examination. Cytology and histology can be used to differentiate between PR and CR in rare cases (e.g., after treatment to differentiate between residual benign lesions and residual malignant lesions in tumor types such as germ cell tumors).

10.2.3 Baseline Documentation of "Target" and "Non-Target" Lesions

All measurable lesions up to a maximum of 2 lesions per organ and 5 lesions in total, representative of all involved organs should be identified as target lesions and recorded and measured at baseline. Target lesions should be selected on the basis of their size (lesions with the longest diameter) and their suitability for accurate repeated measurements (either by imaging techniques or clinically). A sum of the longest diameter (LD) for all target lesions will be calculated and reported as the baseline sum LD. The baseline sum LD will be used as reference by which to characterize the objective tumor response. All other lesions (or sites of disease) should be identified as non-target lesions and should also be recorded at baseline. Measurements of these lesions are not required, but the presence or absence of each should be noted throughout follow-up.

10.2.4 Definitions of Tumor Response-Measurable Disease

10.2.4.1 Complete Response (CR)

The disappearance of all known disease, determined by two observations not less than 4 weeks apart. There can be no appearance of new lesions.

10.2.4.2 Partial Response (PR)

A 30% or more decrease in total tumor load of the lesions that have been measured to determine the effect of therapy by two observations not less than 4 weeks apart. There can be no appearance of new lesions or progression of any lesion.

10.2.4.3 Progressive Disease (PD)

At least a 20% increase in the sum of the LD of target lesions, taking as reference the smallest sum LD recorded since the treatment started, the appearance of one or more new lesions and/or an unequivocal progression of non-target lesions.

10.2.4.4 Stable Disease (SD)

Neither sufficient shrinkage to qualify for PR nor sufficient increase to qualify for PD, taking as reference the smallest sum LD since the treatment started.

10.2.5 Definition of Disease Progression

Disease progression will be defined as:

- 1) Radiologic progression of disease by RECIST 1.1 criteria.
- 2) Clinical progression as determined by the investigator, which may be characterized as, but is not limited to:
 - a. Increase of at least 2 points in ECOG performance status attributable to cancer progression.
 - b. Requirement for palliative radiation, chemotherapy or surgery.
 - c. Death from disease progression.

11.0 DOSAGES AND DISPENSATION OF DRUG

11.1 Dispensation of Study Drug

The study drugs are defined as ABT-888, 5FU, and oxaliplatin. Subjects will receive an IV infusion of leucovorin and oxaliplatin on Day 1 of each cycle, according to standard practice. Additionally, subjects will be hooked up to a pump that administers 5FU over 46 hours from Day 1 to Day 3 of each cycle. Subjects will also receive sufficient quantities of ABT-888 for 7 days of administration in each cycle. ABT-888 will be dispensed prior to dosing at each cycle (Day 1 of each cycle). Patients will receive bottles of ABT-888. Subjects will be provided with self-administration instructions and subject diaries to record the date and time they took the ABT-888. Subjects will be instructed to store ABT-888 according to specific directions described below. Subjects

should return bottles of ABT-888 (empty, partially filled or full) and their diaries to the study site prior to each cycle and at the Final Visit.

11.2 Treatments Administered

One cycle will be 14 days. Patients will receive oxaliplatin (85mg/m²) and leucovorin (400mg/m²) on day 1, followed by a continuous infusion of 5FU (2400mg/m²) over 46 hours on days 1-3. Patients will also receive ABT-888 twice-a-day on Days 1-7 of each 14-day cycle. The dose of ABT-888 in the Phase I portion will be set according to the cohort level. The dose in the Phase II portion of the study will be 200mg orally twice a day. The evening dose of ABT-888 will be taken approximately 12 hours after the morning dose, both doses with or without food. Abbott will supply ABT-888 capsules.

11.2.1 Packaging and Labeling

11.2.1.1 ABT-888

ABT-888 is supplied as 20, 40, or 50mg tablets. ABT-888 will be packaged in bottles containing sufficient capsules for 8 days of therapy per cycle (which includes 1 extra day's worth of pills).

11.2.1.2 ABT-888 Liquid Formulation

For patients who cannot take oral medications and require feeding through a PEG tube (or by mouth, but liquid only), a dose equivalent liquid formulation is available that has been tested and proven to be of equivalent potency. The liquid formulation may be supplied on an as needed basis.

- a. The Liquid formulation is supplied as a 10mg/ml liquid
- b. Patients will be supplied with pre-filled syringes containing the proper dose (e.g. 14 syringes for 7 days of BID treatment)
- c. Dose modifications will be modified by filling syringes with only the proper amount of medication to meet the dose modification
- d. Patients will continue to note compliance in the patient diary, but the notations will be for the syringes used, rather than the pills taken
- e. The used and unused syringes should be returned to the nurse prior to the next dosing for documentation of compliance.

11.2.1.3 Bottle Labels

Each bottle will be labeled with an open-label white single panel or booklet label that will include, but is not limited to, the following information:

- 1) Protocol number
- 2) Drug identification
- 3) Lot number
- 4) Number of capsules
- 5) Storage conditions
- 6) Dosing instructions
- 7) Blank spaces to write the subject's identification number, initials and date dispensed

Each bottle label must remain affixed to the bottle.

11.2.2 Storage and Disposition of Study Drug

11.2.2.1 ABT-888

ABT-888 and placebo must be stored at 15° to 25°C (59 to 77°F). Excursions are permitted up to 30°C (86°F).

All clinical supplies must be stored in a secure place until they are dispensed for subject use or are returned to Abbott. Investigational products are for investigational use only, and are to be used only within the context of this study. The clinical supplies supplied for this study must be maintained under adequate security and stored under conditions specified on the label. If pre-arranged between Abbott and the site, destruction of used and unused study drug will be performed at the site.

11.2.3 Treatment Compliance

Subjects will be instructed to return all ABT-888 bottles (empty, partially filled or full) to the study site personnel prior to each cycle and at the Final Visit. The study site personnel will document the bottles of study drug

returned and the number of capsules per bottle, according to institutional policy. If the number of capsules taken and the number of capsules returned do not add up to the number of capsules dispensed, an explanation will be provided. Unless otherwise directed by the principal investigator, a subject will be considered compliant with study drug, ABT-888, if 80% of the assigned dose is taken during a cycle.

11.2.4 Drug Accountability

The investigator or designee will verify that ABT-888 supplies are received intact and in the correct amounts. A signed and dated Proof of Receipt (POR) or similar document will support documentation of the receipt of supplies. An accurate running inventory of ABT-888 will be maintained by the site, and will include the lot number, POR number(s), the bottle numbers, and the date study drug was dispensed for each subject. Upon completion or termination of the study, all original containers (empty or containing unused study drug) will be returned to Abbott according to instructions from Abbott or, if pre-arranged between Abbott and the site, destruction of used and unused study drug will be performed at the site. Labels must remain attached to the containers. The investigator or his/her designated representative agrees not to supply study medication to any persons not enrolled in the study or not named as a sub-investigator. The site will record the lot number and dose of ABT-888 given to each subject.

11.2.5 Selection of Doses in the Study

The standard doses of 5FU and oxaliplatin are part of the modified FOLFOX-6 regimen as detailed above. These are the standard doses used in patients with colon cancer, in particular, but are also used in patients with several other cancer types. These doses will not be compromised, unless the patient experiences toxicities requiring dose reductions.

The starting dose of ABT-888 (40mg) is derived from the Phase 1 trial of ABT-888 in subjects with Non-Hematologic Malignancies (NHM) and Metastatic Melanoma (MM). ABT-888 pharmacokinetic results following the 20 and 40 mg BID doses achieved the steady-state exposures (AUC) that were effective in murine efficacy models. However, newer information available from Abbott, but as yet unpublished states that greater anti-cancer efficacy is seen with higher doses of ABT-888. Thus, the Phase I portion of this trial aims to assess the maximally tolerated dose of ABT-888. The dose of 40mg of ABT-888 is being applied in several other Phase II studies in combination with multiple other chemotherapy regimens.

12.0 CORRELATIVE RESEARCH AND TUMOR BIOPSIES

The premise that underlies the use of this combination is that 5FU and oxaliplatin (primarily oxaliplatin) will induce significant DNA damage, and that pancreatic cancer cells, in which PARP is activated, will be particularly dependent upon PARP activity to recover from the oxaliplatin-induced DNA damage. Thus, concurrent inhibition of PARP will result in overwhelming DNA damage in cancer cells, ultimately leading to increased cancer cell death. Tumors that have other abnormalities in the DNA-repair pathway may be even more susceptible to this combination. It is possible that tumors that exhibit these deficiencies will be particularly sensitive to DNA damage and PARP inhibition, which may predict for an increased ORR with therapy. Thus, we will perform a correlative analysis of BRCA2 related gene germline mutations from patient specimens, as well as screen the expression of a panel of DNA repair genes (Table 7) in patient tumor samples. All patients will undergo a fresh, pre-treatment tumor biopsy unless it is technically not feasible.

Also, all patients will be required to undergo a tumor biopsy upon disease progression to assess the mechanisms of resistance to PARP inhibitor-based therapy.

Finally, serial plasma samples for patients will be collected prior to treatment on C1 D1; C1, D7; and concurrent with each restaging study. 5 mL of blood will be collected via venipuncture (venipuncture is preferred, however if an indwelling catheter must be used, 3 catheter volumes of blood must be collected and discarded prior to collection of the sample) into evacuated tubes containing potassium EDTA. Immediately after collection, the tubes will be inverted 8 to 10 times to ensure good mixing of blood and anticoagulant and placed in an ice bath. The date and time of collection for each sample will be recorded. The complete process of centrifugation, transfer to polypropylene tubes and freezing should be accomplished within 60 minutes from blood draw. The processing of should be performed as described below:

1. Immediately invert the collection tubes 8 to 10 times.
2. Centrifuge sample at 1100 to 1300 × g for 10 minutes at 2° to 8°C to separate the plasma.

3. Transfer plasma using plastic pipettes into screw-capped polypropylene tubes labeled with the patient number, the protocol number, and the study period and/or study day.

4. Store samples at -20°C or colder in [name] lab.

Samples collected outside of Georgetown University can be batched, but ultimately must be shipped to [name] on dry ice at:

Lombardi Comprehensive Cancer Center

c/o [name], PhD

[name]

[name]

Importantly, the correlative studies will take place at Georgetown University under the guidance of [name]; and/or at Thomas Jefferson University under the guidance of [name]; and/or samples may be outsourced to a third party vendor (e.g. Tempus) for additional analysis.

- All correlative samples will have been de-identified prior to testing, as per Section 12.4 below.

Secondary Scientific Objectives: To correlate the response rate of ABT-888 plus 5FU and oxaliplatin to:

- 1) Tumors that have decreased expression of or mutations in BRCA-1 or -2
- 2) PARP activity levels in serial tumor samples
- 3) Expression levels of DNA repair enzymes in tumor tissues
- 4) Pharmacokinetic and pharmacogenomic parameters associated with the metabolism of ABT-888
- 5) As well as to isolate and propagate tumor cell lines obtained from patient samples and circulating tumor cells

12.1 Tumor Biopsies and Serial Tumor Biopsies

For all patients for the pre-treatment and post-treatment (progression) tumor biopsies, needle biopsies will be obtained prior to therapy (Screening or prior to dosing on C1D1). An 18-20 gauge needle will be used. At least three 1-2cM core biopsies should be obtained. All samples should be labeled with the date, protocol number, protocol assigned patient number, and biopsy number (1 – pre-treatment; 2 – post-treatment). One sample will be placed in a cryotube and snap frozen in liquid nitrogen. The sample will be stored in liquid nitrogen in the Lombardi Cancer Center. The second and third samples will be placed in formalin, and submitted to the histopathology and tissue shared resource in the Lombardi Cancer Center for tissue embedding. The tumor block will be stored in the lab of [name]. Samples collected outside of Georgetown University can be batched, but ultimately must be shipped to [name] on dry ice at:

Lombardi Comprehensive Cancer Center

c/o [name], PhD

[name]

[name]

Of note, patients who are on chronic anticoagulation will be required to hold anticoagulation prior to the biopsies being performed. Patients on warfarin must hold treatment for 5 days, but will be on low-molecular weight heparin (LMWH), 1mg/kg sub-cutaneously twice a day. The LMWH will continue until the last biopsy is complete. Patients may then resume warfarin the day after the last biopsy. Additionally, patients on LMWH will hold (i.e., not receive) the dose of LMWH the morning of the procedure, but will resume the LMWH the evening of the day of the biopsy.

12.2 PARP Activity Levels

One core sample will be assayed to evaluate PARP inhibition. Tumor samples will be assayed using an enzyme-linked immunosorbent assay (ELISA) to evaluate PARP inhibition, and exploratory analysis will be performed to correlate the results with clinical outcomes.

12.3 Assessment of BRCA-1 and -2 mutations, PARP activity, and Expression of DNA repair enzymes

12.3.1 Tumor Block Submission

Formalin-fixed, paraffin embedded tissue blocks will be used for analysis. If blocks cannot be submitted, 1 H&E stained slide and 10 unstained slides of a 4 micron section mounted on positively-charged glass slides from each type of block (mucosa and tumor) are acceptable. Two separate formalin-fixed, paraffin embedded tissue blocks must be submitted: one block with **normal mucosa and one block with resection tumor**. (One block with both normal mucosa and tumor is acceptable if 2 blocks cannot be obtained).

12.3.2 Cancer Cell Isolation

Tumor specimens will be used to isolate components of the pancreatic cancer (tumor cells and stromal cells). This will be accomplished by using laser capture microdissection either on frozen or paraffin materials.

12.3.3 Familial and High Likelihood Screening

First any patients, based on family history, who qualify as having the familial form of pancreatic cancer will go through a systematic screening process (Figure 5)(22). Our strategy includes the following screen. A) Genomic DNA of patients with a history of *BRCA2* mutations in their families (based on previous work(22)) will be sent for sequencing (based on their medical insurance) to Myriad Genetics (Salt Lake City, UT). B) Patients with at least 2 or more relatives that have been diagnosed with pancreatic, ovarian, or breast cancers will be screened by a real-time PCR based assay that will test for expression levels of the clinically informative DNA repair genes in this study (*BRCA1*, *BRCA2*, *FANCC*, and *FANCG*). Recently, a novel gene, *PALB2*, was directly linked to familial pancreatic cancer and the protein is a binding partner of *BRCA2*(9). Although the significance of this finding as it relates to targeted therapy is still being explored, *PALB2* will still be included in the screening process, because in theory tumors mutated in *PALB2* will be sensitive to our targeted therapeutic strategy. The template for these assays will be isolated RNA (using the Qiagen RNAeasy kit) from laser capture microdissected (LCM) tumor cells. C) Any suggestive loss of expression of any of these genes will allow us to move to the next step of direct sequencing of the specific gene (s) (i.e., *PALB2*, *BRCA2*, *FANC* and *G*) whose expression in the tumor cells has been lost. Sequencing templates will be PCR amplified products from LCM gDNA samples isolated (DNAeasy, Qiagen) and amplified from LCM pancreatic cancer tumor cells (to detect alterations in both alleles). We are experienced in depicting the components of pancreatic cancer tissue(23).. Finally, 'sporadic' pancreatic cancer patients who have an objective partial or complete response (as defined by RECIST criteria) will be put through a similar screening strategy as described above. Our hypothesis is that patients with a defined molecular 'BRCA-deficiency' will be part of our responder group. Further, our serial biopsy specimens will be screened as described in this task.

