12.3.4 Defining a novel response signature

RNA samples obtained as described above will be used as a resource to study a, logical focused group of DNA repair pathway genes that have been shown to be good candidate targets (see Table 7). We will use the samples processed above with Super Array technology (SA Biosciences) to screen for a putative molecular signature from their pathway specific array (DNA repair). These platforms are based on straightforward real-

time, optimized PCR technology which includes a web-based program that performs statistical, data analysis. As noted PARP-1 and related genes are all part of this condensed array platform. If other related DNA repair genes emerge in the literature, we will add them to our platform immediately.

Table 7: DNA Repair Enzymes to be Analyzed (SA Biosciences):

Enzyme Class	Specific Gene Abbreviations
Damaged DNA Binding	Brca1, Brca2, FANCC, FANCG, FANCF Ercc1, Ercc2, H2afx, Msh2, Msh3, Rad1, Rad51, RGD1563765 (Rad51c), RGD1564823 (Xrcc2), Rad51l1, Trpc2, Xpa, Xpc, Xrcc1, Rad1, Rad9, RGD1566025 (Pinx1), Smc1l1 (Smc1a), Tp53. Base-excision Repair: LOC680915 (Mbd4), Mpg, Mutyh, Nthl1, Ogg1, Parp1 (Adprt1), Parp2 (Adprt1), RGD1308665 (Mare)
Base-excision Repair	LOC680915 (Mbd4), Mpg, Mutyh, Nthl1, Ogg1, Parp1 (Adprt1), Parp2 (Adprt1), RGD1308665 (Mare).
Nucleotide-excision Repair	Dclre1a, Fancc, Nthl1, Rad23a, Slk, Xpa, Xpc
Double-strand Break Repair	Brca2, H2afx, Mre11a, Prkdc, Rad52, Xrcc6 (G22p1)
Mismatch Repair	MGC72584 (Pms1), Mlh1, Mlh3, Msh2, Msh3, Pms2, Pold3, Trex1
Other Genes Related to DNA Repair	Apex1, Atm, Atrx, Cry2, Cspd6 (Smc3), Exo1, Fen1, Gtf2h1, Gtf2h2, Lig1, LOC363333 (Chaf1a), LOC685491 (Rbbp4), LOC691105 (Fancg), Mgmt, Mif, Pold1, Pole, Polh, Poli, Polk, Pttg1, Rad17, Rad18, MGC116373 (Rad21), Rad50, Rad9, Rad9b, Rbm4, Rev1l, Smc1l1 (Smc1a), Srd5a2, Sumo1, Tdg, Tnp1, Ube2a, Ung, Wrn, Wrnip1, Xrn2, ERCC1, ALD6IP6, SSBP2

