13.5 Analysis Plan

The primary and secondary efficacy analyses will be performed on all subjects in the study, except for the secondary efficacy analyses which are being performed in only a subgroup of patients. Subjects who have experienced an adverse event or have received at least one cycle of the study drugs (ABT-888 and 5FU and oxaliplatin) will be included in the safety analysis.

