13.5.2 ORR Comparisons

13.5.2.1 ORR in patients whose tumors evidence decreased expression of or mutations in BRCA-1 or -2

ORR will be compared in patients whose tumors demonstrate evidence of decreased expression of or mutations in BRCA-1 or -2 in both pre-and post-treatment samples.

13.5.2.2 ORR in patients as a function of the PARP activity level in pre and post-treatment tumor samples

ORR will be compared in patients whose tumors exhibit low vs. high PARP activity level (as defined in section 5) in both pre-and post-treatment samples. However, for statistical purposes, only 10 patients will be evaluated for PARP activity. Thus, this efficacy endpoint will be considered as a pilot, hypothesis-generating endpoint only.

13.5.2.3 ORR in patients as a function of the expression levels of DNA repair enzymes in tumor tissues in pre and post-treatment samples

ORR will be compared in patients whose tumors exhibit low vs. high levels of the various DNA repair enzymes listed in Table 7 in both pre-and post-treatment samples. However, for statistical purposes, only 10 patients will be evaluated. Thus, this efficacy endpoint will be considered as a pilot, hypothesis-generating endpoint only.

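### BRCA screening of sporadic patients is triggered by response, so the planned ORR comparison by BRCA status is biased, in a direction that depends on an unstated rule for untested patients

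*Combined protocol and SAP*

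**What the plan says.** Section 12.3.3 sets out who is screened for loss of BRCA-pathway genes. Rule A sends patients with a family history of BRCA2 mutation for sequencing. Rule B is based on affected relatives: "Patients with at least 2 or more relatives that have been diagnosed with pancreatic, ovarian, or breast cancers will be screened" by an expression assay, with sequencing if expression is lost. Neither rule depends on outcome. For patients the section calls sporadic, the trigger is the outcome itself: "pancreatic cancer patients who have an objective partial or complete response (as defined by RECIST criteria) will be put through a similar screening strategy". The next sentence gives the expectation: "Our hypothesis is that patients with a defined molecular 'BRCA-deficiency' will be part of our responder group".

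Section 13.5.2.1 plans the comparison: "ORR will be compared in patients whose tumors demonstrate evidence of decreased expression of or mutations in BRCA-1 or -2", in pre- and post-treatment samples. It names no comparator group, does not restrict how patients came to be tested, and does not say how untested patients are classed.

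Other passages point to wider testing. Section 12.0 says "All patients will undergo a fresh, pre-treatment tumor biopsy unless it is technically not feasible", and plans to "screen the expression of a panel of DNA repair genes (Table 7) in patient tumor samples". Section 2.6 says much the same. Neither sets a response condition. Section 12.3.3 itself ends by saying that serial biopsy specimens will be screened too. Section 12.3.4, however, says "RNA samples obtained as described above will be used as a resource" for the DNA-repair array, which read literally refers back to the patients selected in 12.3.3.

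**The concern.** Under the 12.3.3 rule, a sporadic patient with a BRCA-deficient tumour enters the known-deficient group only by responding. Exposure status then depends on the outcome with which it is to be compared, so the ORR in that group is too high even if BRCA status has no influence on response.

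This comparison serves the first-listed secondary scientific objective (Sections 2.4.2.2 and 7.2.2). Sections 13.5.2.2 and 13.5.2.3 are labelled as pilot and hypothesis-generating; 13.5.2.1 carries no such label. A biased result here could be taken as support for, or evidence against, selecting patients by BRCA status in a later trial.

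**Working it through.** **The plan's own figures.** The plan gives none for the BRCA comparison. Its only ORR design figure is the Simon design (9 then 24 patients, at least 1 and then at least 3 responders). The probability of success is the sum over x = 1 to 9 of P(Bin(9,p) = x) × P(Bin(15,p) ≥ 3 − x). This gives 0.0931 at p = 5% and 0.9028 at p = 25%, matching the stated 10% and 90%. Nothing below affects it.

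**Inputs.**
- True ORR q is the same in deficient and proficient patients (no BRCA effect). The main case is q = 25% and the check is q = 5%, the two design values in Section 13.3.
- Prevalence of BRCA-pathway mutation: Section 5.2 gives 5–10% in sporadic tumours and over 15% in familial cases. The main case uses pF = 15% and pS = 10%. Section 13.5.2.1 also counts decreased expression, so the true figures may be higher.
- Sporadic share s: the documents give none, so it is varied.
- All familial patients are tested. Sporadic patients are tested only if they respond.

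**Formulas**, per enrolled patient.
- Known deficient: D = (1−s)·pF + s·q·pS
- Responders among them: R = (1−s)·pF·q + s·q·pS
- ORR in known deficient = R/D
- Comparator, untested counted as negative: (q − R)/(1 − D)
- Comparator, untested excluded: [(1−s)(1−pF)q + s·q(1−pS)] / [(1−s)(1−pF) + s·q(1−pS)]

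**Worked case, s = 50%, q = 25%.** D = 0.5×0.15 + 0.5×0.25×0.10 = 0.0875. R = 0.01875 + 0.0125 = 0.03125. R/D = 35.7%. Untested as negative: 0.21875/0.9125 = 24.0%. Untested excluded: (0.10625 + 0.1125)/(0.425 + 0.1125) = 0.21875/0.5375 = 40.7%.

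| q | s | pF / pS | ORR, known deficient | Comparator, untested = negative | Comparator, untested excluded |
|---|---|---|---|---|---|
| 25% | 20% | 15% / 10% | 28.0% | 24.6% | 29.7% |
| 25% | 50% | 15% / 10% | 35.7% | 24.0% | 40.7% |
| 25% | 80% | 15% / 10% | 55.0% | 23.4% | 63.6% |
| 25% | 50% | 15% / 5% | 30.8% | 24.5% | 41.4% |
| 25% | 50% | 10% / 10% | 40.0% | 24.0% | 40.0% |
| 25% | 50% | 50% / 10% | 28.6% | 23.7% | 48.3% |
| 5% | 50% | 15% / 10% | 8.1% | 4.7% | 9.8% |

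The known-deficient ORR exceeds q in every row, whichever handling is used. Counting untested patients as negative creates a false BRCA effect. Excluding them inflates both groups: the contrast is null when the two prevalences are equal and reversed when the familial prevalence is higher. If everyone is tested regardless of response, both groups have an expected ORR of q (25% v 25%).

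**Who can fall under the response trigger.** Since April 2013, entry needs a known mutation or a suggestive history (Section 8.2.1, criterion 2). Several entry routes satisfy neither rule A nor rule B: personal breast cancer diagnosed at 45 or younger, personal epithelial ovarian cancer, or a family mutation in BRCA1, PALB2 or a FANC gene (rule A names only BRCA2). Phase I patients (estimated 24, Section 13.3) who enrolled before the change add to these. Section 13.2 keeps Phase I patients treated at the Phase II dose out of the Simon assessment, but no text explicitly removes Phase I patients from 13.5.2.1.

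**The case against.** The strongest reply is that the trigger may not govern who ends up with a BRCA result. Pre-treatment biopsies are planned for all patients where feasible, with a further biopsy at progression. The Table 7 panel includes BRCA1, BRCA2, FANCC and FANCG. The registration form asks for a genetic test summary, which precedes any response. A reader might infer from 12.3.3 that deficient sporadic non-responders are never found; the documents do not support that. What stands is that 12.3.3 states a response-dependent rule, 12.3.4 appears to draw its RNA from the same patients, and nothing says which text controls.

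A reader might also infer that the bias necessarily favours the stated hypothesis. It does so only if untested patients count as negative. Section 13.5 can be read that way ("The primary and secondary efficacy analyses will be performed on all subjects in the study"), but the same sentence exempts secondary analyses done in a subgroup, and a comparison that needs tumour results could well be one. That exemption also leaves open whether Phase I patients are included.

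The 2013 eligibility change does narrow the affected group. Ashkenazi descent, for example, is not an entry route of its own; it only qualifies a personal history of breast cancer. With 20% sporadic and untested counted as negative, the false gap is about 3 points (28.0% v 24.6%). The change shrinks the problem without removing it.

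**Conclusion.** The point holds as one of outcome-dependent ascertainment. If 12.3.3 is followed as written, the ORR in known-deficient patients is inflated under either handling of untested patients: 28.0% at 20% sporadic and 35.7% at 50%, against a true 25%. The sign of the contrast is undetermined because the plan does not say how untested patients are classed: 35.7% v 24.0% one way and 35.7% v 40.7% the other, at 50% sporadic. Neither is a valid estimate.

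The sizes rest on the assumed sporadic share and on prevalences taken from the ranges in Section 5.2. The existence of the bias needs only that some deficient sporadic patients enter the comparison through the response trigger. Confidence is medium, because Sections 2.6 and 12.0 may intend testing of everyone. The matter is confined to a secondary scientific objective and gives no ground for doubting the primary ORR analysis or the Simon design.

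**What to change.** In 13.5.2.1, restrict the ORR comparison to patients whose BRCA status was determined without regard to response: rules A and B of 12.3.3, or status known at entry. Define deficient, proficient and unknown groups, class everyone else as unknown, and list response-triggered results separately as case descriptions. State whether Phase I patients are included.

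Alternatively, if baseline tissue from all patients is to be assayed, as 2.6 and 12.0 suggest, apply one screen to all of it, blind to response, and delete the trigger in 12.3.3. Either way, reconcile 2.6, 12.0, 12.3.3, 12.3.4 and 13.5.2.1 so that they give the same rule.

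The first option is a change of wording only, with no new biopsy or assay. Its cost is fewer patients in a secondary comparison. For illustration, with the maximum of 72 patients (24+48) and half sporadic, the comparison falls from up to 72 patients to 36. The expected number of known-deficient patients falls only from 72 × 0.0875 = 6.3 to 36 × 0.15 = 5.4. The second option keeps more patients, but needs the screen run on the baseline tissue of sporadic non-responders if that is not already intended.
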